38 1) Change in clinical status as captured by 7-point ordinal scale score (being utilized in Gilead Sciences
39 remdesivir trial^{19, 20}) at time of plasma infusion (day 0) compared to day 7:

40

- 44 1. Death
- 45 2. Hospitalized, requiring mechanical ventilation or ECMO

- 1 3. Hospitalized, requiring non-invasive ventilation or high flow oxygen
- 2 4. Hospitalized, requiring supplemental oxygen
- 3 5. Hospitalized, not requiring supplemental oxygen--requiring ongoing medical care
- 4 (COVID-19 related or otherwise)
- 5 6. Hospitalized, not requiring supplemental oxygen-not requiring ongoing medical care
- 6 (COVID-19 related or otherwise).
- 7 7. Not Hospitalized

8 2) Adverse events related to plasma infusion (within 6 hours of infusion) to include²³:

- 9 a) Transfusion-related events
 - 10 i. Transfusion Associated Circulatory Overload
 - 11 ii. Transfusion-Related Lung Injury
 - 12 iii. Allergic Reaction/Anaphylaxis
 - 13 iv. Transmission of transfusion transmitted diseases
 - 14 v. Febrile Transfusion Non-hemolytic Transfusion Reaction

15 Secondary Endpoints:

- 16 3) Change in 7-point ordinal scale score (being utilized in Gilead Sciences remdesivir trial) from time
- 17 of plasma infusion (day 0-prior to first infusion) to days 14, 21, and 28^{19,20}.
- 18 4) SOFA score at days 0, 7, 14, 21, 28²¹
- 19 5) Time to discontinuation of supplemental oxygen
- 20 6) Duration of hospitalization
- 21 7) Time to liberation from mechanical ventilation (for patients on a ventilator)
- 22 8) Need for mechanical ventilation (For those not on the ventilator)
- 23 9) All-cause Mortality [at 28 days]

24 ○

| Organ System, Measurement | SOFA Score | | | | |
|--|------------|-------------------|--|--|---|
| | 0 | 1 | 2 | 3 | 4 |
| Respiration PaO ₂ /FiO ₂ , mmHg | Normal | <400 | <300 | <200 (with respiratory support) | <100 (with respiratory support) |
| Coagulation Platelets x10 ³ /mm ³ | Normal | <150 | <100 | <50 | <20 |
| Liver Bilirubin, mg/dL (μmol/l) | Normal | 1.2-1.9 (20-32) | 2.0-5.9 (33-101) | 6.0-11.9 (102-204) | >12.0 (<204) |
| Cardiovascular Hypotension | Normal | MAP<70 mmHg | Dopamine ≤5 or dobutamine (any dose)** | Dopamine >5 or epinephrine ≤0.1 or norepinephrine ≤0.1 | Dopamine >15 or epinephrine >0.1 or norepinephrine >0.1 |
| Central Nervous System Glasgow Coma Score | Normal | 13-14 | 10-12 | 6-9 | <6 |

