| Renal Creatinine, mg/dL (μmol/l) or Urine output | Normal | 1.2-1.9 (110-170) | 2.0-3.4 (171-299) | 3.5-4.9 (300-440) or <500 mL/day | >5.0 (>440) or <200 mL/day |

26 * Source: [Vincent et al., 1996](#).

- 27 10) All other adverse and serious adverse events will be recorded as well (see adverse events section to follow).
- 28 11) Change in standard of care inflammatory markers (ferritin, LDH, CRP, D-dimer) where available
- 29 from day 0 to days 7, 14, 21, 28.

1 Exploratory Endpoints:

2 12) Association between antibody levels and donor characteristics/clinical course
3 13) Association between clinical response in recipients and antibody levels in the donors

4

5 **Dosing:**

6 • One dose of 200-300mL (standard collection bag volume) of convalescent plasma will be infused
7 over approximately one hour intravenously with standard vital sign monitoring per unit protocol
8 and standard of care for plasma infusion.

9 • Up to two additional doses of 200 mL of convalescent plasma may be administered within 14 days of initial
10 dose at 1-7 day intervals according to disease severity and tolerance of the infusions. Where possible,
11 plasma from distinct donors will be used for additional doses.

12 • To reduce probability of allergic reaction, pre-medication with diphenhydramine 25mg orally or
13 intravenously will be given within 2 hours before each dose of plasma, unless there is a
14 contraindication noted by treating physician.

15 • Slower infusion time of two hours with optional dose of 20mg intravenous furosemide after first
16 hour can be considered for patients at risk for transfusion-associated circulatory overload

17 • Infusion can be slowed for patient comfort at any time.

18 **Safety:** Patients will be monitored closely during plasma infusion per Inova nursing policy titled
19 “Transfusion/Infusion of Blood Components” Version 01.01. Patients will remain in the hospital for a minimum
20 of 24 hours post-infusion with vital signs performed per standard of care with frequency based on the
21 treating hospital unit. Patients will be discharged from hospital according to standard of care any time
22 after completion of 24 hour observation period post-infusion dosing.

23 If oxygenation worsens post-infusion, treating physician will perform assessment as to the presence of a
24 transfusion related reaction, increase oxygen delivery, and obtain portable chest film if deemed clinically

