25 appropriate. Treating physician will notify the study doctor and staff if there is an adverse reaction.

26 Possible anticipated infusion related reactions could include:

27 1) Transfusion Associated Circulatory Overload – dose of intravenous furosemide may be
28 considered
29 2) Transfusion-Related Lung Injury- supportive care as directed by treating physician
30 3) Allergic Reaction/Anaphylaxis – additional dose of diphenhydramine, dose of intravenous or oral
31 corticosteroids or intramuscular epinephrine could be considered
32 4) Transmission of transfusion transmitted diseases – supportive care or targeted treatment if
33 infection identified
34 5) Febrile Transfusion Non-hemolytic Transfusion Reaction – supportive care

35 These adverse events, if present, will be recorded by clinical research team.

36

37 **Post-Treatment Blood Draws:**

38 Optional blood draws (up to four tubes) may be drawn on days 7, 14, 21, and 28 (+/2 days) following each
39 dose of convalescent plasma where feasible for Biobanking.

40 If patient is discharged prior to 7 days post-dosing, then follow-up phone call or email assessments
41 will be made by study staff at 7 days, 14 days, 21, and 28 days (+/2 days) following the original dose.

1
2 **Script for Phone Call(s) or Email(s) to Recipients (if applicable):**

3 1) Are you in a home environment (your home or family member's home)?
4 2) If not, are you in a nursing or rehabilitation facility?
5 3) Are you using oxygen?
6 4) Have you required an urgent care or emergency room visit for any reason since your
7 discharge?
8 5) Have you required re-hospitalization for any reason since your discharge?

9
10 **Trial Methods**

11 Convalescent plasma will be made available to patients hospitalized in the Inova Heath System.

12
13 Patient outcome monitoring and reporting will include indicators of safety and efficacy. Case Report
14 Forms will be used to capture essential data.

15
16 **Statistical Plan**

17 Study parameters (e.g., clinical status scale, death, hospitalization, etc.) will be described using traditional
18 descriptive statistics (median [IQR], frequency and percent). Data will be assessed for 'missingness' with
19 parameters exceeding 10% missing explored for imputation (e.g., multiple imputation, last value carried
20 forward, etc.). Departures from normality will be assessed via Shapiro-Wilkes test with data

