13 investigational product, whether or not considered related to the investigational product. AEs may also
14 include pretreatment or posttreatment complications that occur as a result of protocol specified procedures
15 or special situations.

16 **Serious Adverse Events (SAE)**

17 A SAE is defined as an event that, at any dose, results in the following:

18 1) Death
19 2) Life-threatening (Note: The term “life-threatening” in the definition of “serious” refers to an event
20 in which the subject was at risk of death at the time of the event; it does not refer to an event that
21 hypothetically might have caused death if it were more severe.)
22 3) In-patient hospitalization or prolongation of existing hospitalization
23 4) Persistent or significant disability/incapacity
24 5) A congenital anomaly/birth defect
25 6) A medically important event or reaction: such events may not be immediately
26 7) Life-threatening or result in death or hospitalization but may jeopardize the subject or may require
27 intervention to prevent one of the other outcomes constituting SAEs. Medical and scientific
28 judgment must be exercised to determine whether such an event is a reportable under expedited
29 reporting rules. Examples of medically important events include intensive treatment in an
30 emergency room or at home for allergic bronchospasm; blood dyscrasias or convulsions that do
31 not result in hospitalization; and development of drug dependency or drug abuse.
32

33 **Data Storage and Records Retention** Information about study subjects will be kept confidential and
34 managed according to the requirements of the Health Insurance Portability and Accountability Act of
35 1996 (HIPAA). Data will be stored in a secure electronic database during and after the study and will not
36 be shared with unauthorized persons. Subjects will be de-identified in the database. Each subject will have
37 a unique identification number that will be maintained in a separate database. The principal investigator,
38 co-investigators, and authorized clinical research personnel will have access to the data to perform the
39 retrospective chart review to verify COVID-19 test result(s) and details of the index COVID-19
40 hospitalization (with regards to blood transfusion and blood type), if applicable. For the protection and
41 privacy of the patients, no identifying information will be released.
42

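### Post-discharge calls are scheduled only for recipients discharged within 7 days of dosing, although the day 14 to 28 ordinal score and 28-day mortality are endpoints for every recipient

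*Combined protocol and SAP*

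**What the plan says.** The follow-up rule for recipients stands under Post-Treatment Blood Draws. It reads "If patient is discharged prior to 7 days post-dosing, then follow-up phone call or email assessments" and continues "will be made by study staff at 7 days, 14 days, 21, and 28 days (+/2 days) following the original dose".

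The other relevant text is:

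- **Secondary Endpoints, items 3 and 9.** The ordinal score is compared from the time "of plasma infusion (day 0-prior to first infusion) to days 14, 21, and 28", and all-cause mortality is taken at 28 days. Neither is restricted by date of discharge.
- **Statistical Plan, secondary endpoints.** The ordinal score is analysed by individual growth models at days 0, 14, 21 and 28. Mortality is tested by chi-square against a hypothesized 1-5% (age adjusted).
- **Statistical Plan, opening paragraph.** Imputation is to be explored for parameters with more than 10% missing. Multiple imputation and last value carried forward are given as examples.
- **Post-Treatment Blood Draws.** "Optional blood draws (up to four tubes) may be drawn on days 7, 14, 21, and 28 (+/2 days) following each" dose, for biobanking and only where feasible.
- **Secondary Endpoints, item 10, and the SAE definition.** "All other adverse and serious adverse events will be recorded as well"; the definition includes death and "In-patient hospitalization or prolongation of existing hospitalization".
- **Trial Methods.** "Patient outcome monitoring and reporting will include indicators of safety and efficacy. Case Report" Forms are to hold the essential data.
- **Dosing and Safety.** Up to two further doses may follow within 14 days of the first, and each recipient stays in hospital for at least 24 hours after infusion.

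**The concern.** The endpoints apply to everyone treated, but the only scheduled contact after discharge applies to those who left early. Followed as written, whether a later outcome is collected depends on when the patient went home. Time to discharge is itself an outcome, since duration of hospitalization is also a secondary endpoint.

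The study has no concurrent control. Mortality is set against a fixed reference, so an error in ascertainment passes straight into the comparison. Its direction depends on a choice the plan leaves open:

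- Counting uncontacted patients as alive, or carrying category 7 (not hospitalized) forward, misses late deaths and readmissions and leans toward benefit.
- Dropping them inflates mortality whenever their death rate is below that of the other recipients.

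**Working it through.** The plan states no figure for expected missingness, so there is nothing to reproduce. The check sets the call rule against the endpoint times and then asks what one missed outcome is worth.

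**1. Who falls outside the rule.** Let D be the day of discharge and L the day of the last dose, both counted from the original dose. L is 0 for a single dose and at most 14 under Dosing. The rule does not say which dose starts its 7 days.

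- Original-dose reading: calls are made if D < 7. The gap for time point T is D = 7 to T - 1.
- Last-dose reading: calls are made if D < L + 7. The gap is D = L + 7 to T - 1.

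| Time point | Original-dose reading (and single-dose recipients on either reading) | Last-dose reading, L = 7 | Last-dose reading, L = 14 |
|---|---|---|---|
| Day 14 | days 7-13 | none | none |
| Day 21 | days 7-20 | days 14-20 | none |
| Day 28 | days 7-27 | days 14-27 | days 21-27 |

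The 2-day window is stated only for the calls and the optional draws. If in-hospital assessments shared it, which is not said, the first column would end at T - 3: days 7-11, 7-18 and 7-25.

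On the original-dose reading, a recipient dosed again on day 6 or later cannot leave before day 7, because of the 24-hour stay. All such recipients fall outside the rule.

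**2. Whether another provision fills the gap.**

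- The blood draws are voluntary and record no outcome.
- Case report forms and SAE recording say what is to be captured, but give no source or schedule after discharge.
- The chart review under Data Storage and Records Retention covers test results and the index hospitalization.

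**3. What is not affected.** On either reading, a patient who is not called was still in hospital until day 7 or later, so day-7 status is known. The 6-hour infusion events occur in hospital. Inpatients at a later time point can be scored from the ward record.

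**4. What one outcome is worth.** Inputs are the recipient target of 150-200 and the 1-5% reference.

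- One death counted as alive: 1/150 = 0.67 points; 1/200 = 0.50 points.
- Deaths implied by the reference: 150 x 0.01 = 1.5 to 150 x 0.05 = 7.5; 200 x 0.01 = 2 to 200 x 0.05 = 10. These are nominal, because the reference is age adjusted.
- The 10% missingness threshold is passed at 16/150 = 10.7% or 21/200 = 10.5%.

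**5. Illustration only; every input is assumed.** Take n = 200, 10 deaths outside the gap, 20 or 80 patients in it, and 1% or 5% of those dying by day 28.

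| In gap | Dying | True | Counted alive | Dropped |
|---|---|---|---|---|
| 20 | 1% | 10.2/200 = 5.10% | 10/200 = 5.00% | 10/180 = 5.56% |
| 20 | 5% | 11/200 = 5.50% | 5.00% | 5.56% |
| 80 | 1% | 10.8/200 = 5.40% | 5.00% | 10/120 = 8.33% |
| 80 | 5% | 14/200 = 7.00% | 5.00% | 8.33% |

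The error is 0.1 to 2.0 points too low if these patients are counted as alive, and 0.1 to 2.9 points too high if they are dropped. The table shows the direction of each handling. It does not estimate what will happen in this trial.

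**The case against.** **It is probably a drafting slip.** The sentence says what happens to early dischargees. It does not say that others go uncontacted, and the endpoint list implies that everyone is followed. Staff may call everyone or use health-system records, and the case report forms are not part of the documents. This is fair, but the protocol schedules neither course, and a slip is a reason to correct the sentence.

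**The call script already shows hospital status.** A reader might infer that the script cannot tell whether a patient is in hospital on the assessment day, because item 5 asks only about readmission since discharge. The documents do not support that. Items 1 and 2 ask in the present tense whether the person is in a home or in a nursing or rehabilitation facility; a no to both, with a yes to item 5, points to a current admission. A person who answers is also evidently alive. What remains is that the script offers no proxy or records route for someone who does not answer.

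**The gap is not fixed.** A reader might take days 7-13, 7-20 and 7-27 as applying to everyone. They do so only on the original-dose reading. The sentence mentions the original dose separately when timing the calls, so the last-dose reading is open, and it shortens or removes the gap for multi-dose recipients. The single-dose share is not given.

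**Growth models tolerate incomplete series.** They do, so alive-or-dropped does not describe the ordinal score analysis. But at the listed times, a recipient discharged on days 7-13 and never contacted would contribute only the day-0 score.

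**Conclusion.** The concern stands for the later secondary endpoints. As written, recipients discharged 7 or more days after dosing have no scheduled contact at the remaining time points, while the day 14, 21 and 28 ordinal score and 28-day mortality are defined and analysed for all.

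The supportable size is 0.67 or 0.50 percentage points of mortality per missed death, at 150 or 200 recipients, against a reference equivalent to between 1.5 and 10 deaths. The number of patients in the gap and their death rate after discharge are unknown. A reader might infer from the illustration that mortality will be wrong by 2 points or more; the documents give no basis for that.

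Nor do they support a claim that deaths after discharge would go unrecorded altogether, since SAE recording is promised. What is missing is a scheduled way of learning of them. This should be corrected, but it does not touch the primary endpoints.

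**What to change.** Replace the conditional sentence with:

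> For any recipient discharged before day 28 after the original dose, phone or email assessments will be made at each remaining time point among days 7, 14, 21 and 28 (±2 days) following the original dose.

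This also removes the ambiguity about which dose starts the clock. Add that vital status will be established from a proxy or health-system records when a recipient cannot be reached. A direct question on whether the person is in hospital that day is an optional clarification.

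Cost: three extra calls for discharge on days 7-13, two for days 14-20 and one for days 21-27, by staff who already call early dischargees. The ceiling is 3 x 150 = 450 or 3 x 200 = 600 calls, reached only if every recipient left on days 7-13. Proxy or record checks for non-responders come on top.

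The calls will not supply SOFA after discharge, which cannot be scored by telephone even for patients already being called. The plan should say separately how SOFA is handled from that point.

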19 • 3 purple top tubes and 1 red top tube for routine transfusion transmitted
20 disease testing

21 o Additional two tubes for SARS-CoV-2 antibody testing (if not already
22 collected at screening visit or if initial screen failure with positive NAT
23 nasal swab test in which case may be repeated)

24 o Optional tubes for COVID-19 Inova Biobank specimen (if not already
25 collected at screening visit) to permit retrospective determination of the
26 characteristics of an effective product and dosage regimen

27 • (if not already collected at screening visit)

28 o Up to 1000mL of plasma may be collected in one donation as calculated by the
29 automated collection machine based on patient characteristics (gender, weight,
30 height, point of care complete blood count test results)

31 • Due to secondary binding of calcium by citrate anticoagulant used in the extracorporeal
32 circuit to prevent clotting during plasma collection, calcium carbonate 2000mg total (four
33 Tums tablets) will be given to each patient per protocol.

34 • Replacement fluid will be administered to donors during collection based on calculated
35 volume by TRIMA instrument during automated plasma collection

36 • Monitoring occurs per protocol for standard plasma donation

37

38 4) Follow-Up Phone Call or Email (1-7 days post-donation)

39 **Script for Phone Call or Email to Donors:**

1 1) How have you been feeling since your plasma donation?
2 2) Do you have any new health concerns?
3 3) Do you have any questions for the study team regarding your participation in the study?
4 4) Would you be interested in donating plasma again in 28 days if you are eligible?
5

6 Repeat plasma collections are optional and must be separated by \geq 28 days. Eligibility must be re-
7 evaluated at each collection, and total volume collected each time will be based on assessment at that time
8 in accordance to guidelines for healthy donors.

9 COVID-19 Convalescent Plasma (CCP) collected as part of this clinical trial will be prioritized for use in
10 recipients enrolled in this clinical trial. In the event that the need arises for CCP in patient(s) outside of
11 the clinical trial and the Blood Bank has a donor match of CCP collected under the clinical trial, the Blood
12 Bank will try to accommodate the request, in the best interest of patient care.
13

1 **BIOBANKING:**

2
3 Collection and retention of blood specimens from both donors and recipients (pre- and post-treatment)

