21 transformations explored as needed. All analyses will be conducted using SAS (version 9.4, Cary, NC)
22 with p<0.05, two-tailed considered statistically significant.

23
24 Primary efficacy endpoints:

25 1. Gilead 7-point scale – For each time point (day 0 vs. 7), summary clinical status scores will be
26 calculated. Changes in scores will be subsequently assessed via a generalized linear mixed model
27 with clinical status assessed at day 0 vs. 7. A statistically significant increase of ± 2 points in β
28 from day 0 to day 7 will be considered as evidence of efficacy. A mixed model allows for
29 examination and inclusion of the variance-covariance matrix into the model as a result of expected
30 within-subject serial correlation as a result of repeated assessments over time.
31 2. Plasma transfusion related adverse events will be scored as 1+ vs. 0 and will be assessed via Chi-
32 Square test with a hypothesized distribution of expected AE (using the higher incidence estimate):
33 i. Transfusion Associated Circulatory Overload: 1:1,566 to 1:68 plasma units
34 transfused
35 ii. Transfusion-Related Lung Injury: 1:1,200 to 1:190,000
36 iii. Allergic Reaction/Anaphylaxis: 1-3%
37 iv. Febrile Transfusion Non-hemolytic Transfusion Reaction: 0.1-1%

38
39 Secondary endpoints:

40 1. Change in 7-point ordinal scale score and SOFA score over time will be assessed via individual
41 growth models (IGM). Times will be day0, 14, 21, and 28
42 2. Mortality will be assessed via Chi-Square test with a hypothesized current mortality rate of 1-5%
43 (age adjusted).
44 3. Need for mechanical ventilation for those not ventilator at time of plasma infusion will be
45 assessed via Chi-Square test with a currently available published estimates.

1 4. Time to discontinuation of supplemental oxygen, time to liberation from mechanical ventilation,
2 duration of hospitalization will be summarized as median (IQR) or rates and compared to currently
3 available published estimates.
4
5

6 **ADVERSE EVENTS AND TOXICITY MANAGEMENT**

7 **Definitions of Adverse Events and Serious Adverse Events**

9 **Adverse Events (AE)**

10 An AE is any untoward medical occurrence in a clinical study subject administered an investigational
11 product, which does not necessarily have a causal relationship with the treatment. An AE can therefore be
12 any unfavorable and/or unintended sign, symptom, or disease temporally associated with the use of an

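### The recipient follow-up script takes no dates and asks nothing about new health problems, so home-oxygen stop days are known only to the gap between calls and post-discharge adverse events that led to no urgent, emergency or inpatient care go unprompted

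*Combined protocol and SAP*

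**What the plan says.** **Recipient script.** Script for Phone Call(s) or Email(s) to Recipients has five items: whether the patient is in a home setting, whether in a nursing or rehabilitation facility, "Are you using oxygen", "Have you required an urgent care or emergency room visit for any reason since your" discharge, and "Have you required re-hospitalization for any reason since your discharge". None asks for a date or a reason.

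**Contacts.** Post-Treatment Blood Draws sets them at days 7, 14, 21 and 28, each within 2 days, counted from the original dose. They are stated only for patients discharged before day 7. The Safety paragraph lets discharge follow standard of care once 24 hours of observation are complete; being off oxygen is not stated as a condition.

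**Endpoints.** Secondary Endpoints item 5 is "Time to discontinuation of supplemental oxygen". Item 10 says "All other adverse and serious adverse events will be recorded as well". The adverse event definition extends to "any unfavorable and/or unintended sign, symptom, or disease temporally associated with the use of an" investigational product, whether or not care is sought.

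**Analysis.** Statistical Plan, secondary endpoints item 4, groups the oxygen, ventilator and hospital-stay times. The sentence ends "duration of hospitalization will be summarized as median (IQR) or rates and compared to currently" available published figures. It gives no rule for assigning a stop date and no method for interval-censored times.

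**Donors.** The donor script asks "Do you have any new health concerns". The recipient script has no equivalent.

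**The concern.** A time-to-event endpoint needs an event date, or an analysis that accepts an interval. For a recipient who goes home on oxygen, the script supplies neither a date nor a prompt for one, and the plan does not say how the resulting interval becomes a number in a median. The study has no control arm in which the same measurement error would arise, so whatever convention is chosen at analysis passes directly into the comparison with published times.

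On safety, the plan promises to record all other adverse events, but after discharge it prompts recipients only for those that led to urgent, emergency or inpatient care. People given the investigational product are asked less about their general health than the donors are.

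**Working it through.** The plan gives no figure on this point to reproduce. The check sets the script against the endpoints, then does the interval arithmetic.

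**1. Script against endpoints**

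| Needed | Script provides |
|---|---|
| Day oxygen stopped (item 5) | Current use, yes or no, on the call day |
| Onset and nature of adverse events (item 10) | Urgent care, emergency visit or readmission since discharge, yes or no |
| Adverse events without such care | No item |
| Hospital status on the target day (ordinal scale) | Location on the call day, up to 2 days away |

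**2. Width of the interval.** Consecutive calls are nominally 14 − 7 = 7 days apart. With 2-day windows at each end the gap runs from 7 − 4 = 3 to 7 + 4 = 11 days. The stop day is known only to lie inside it. Before the first call, the interval runs from discharge to that call.

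**3. Delay if the first oxygen-free call is used as the stop date.** This convention is an assumption; the plan states none. With stop days spread evenly over a 7-day gap, the mean delay is 7 / 2 = 3.5 days and the maximum 7. Drawing call days at random within the windows gives 3.66 days, with a maximum of 11. About 3.6 days is a fair summary.

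**4. Number affected.** The target is 150–200 recipients. The share sent home on oxygen is not given. At 20% it is 0.20 × 150 = 30 to 0.20 × 200 = 40 people; at 50% it is 75 to 100.

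**5. Effect on the planned median.** Illustrative model, all inputs assumed: oxygen stop lognormal with median 9.0 days and log SD 0.7; discharge lognormal with log SD 0.5, its median varied to give each home-oxygen share; calls at days 7, 14, 21 and 28 with windows; stop dated at the first oxygen-free call.

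| Share home on oxygen | Median, calls only if discharged before day 7 | Median, calls to all |
|---|---|---|
| 10% | 9.0 | 9.0 |
| 20% | 9.1 | 9.1 |
| 30% | 9.2 | 9.3 |
| 50% | 10.0 | 11.3 |

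The middle column follows the protocol's trigger for calls. It generously credits those discharged on oxygen on or after day 7 with their true stop day, though no contact is stated for them. At low shares the median hardly moves, because recipients still on oxygen at discharge mostly have stop times above the median already.

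**6. Other sources.** Trial Methods names Case Report Forms without giving their content. Data Storage and Records Retention describes chart review for COVID-19 test results and index-hospitalization details. Neither is said to supply post-discharge oxygen dates or adverse events.

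**The case against.** **The plan allows rates.** Item 4 permits a median (IQR) or rates. The proportion off oxygen on days 7, 14, 21 and 28 is something the script can support. This stands. The difficulty is confined to the median (IQR) option, which the plan leaves open without a rule.

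**No direction of bias is planned.** A reader might infer that the endpoint is biased late. The documents do not support that as a flat statement, because nothing says the call date becomes the stop date. What they support is imprecision, with lateness if that convention is adopted.

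**The script does catch events.** A reader might also infer that non-serious adverse events after discharge are not collected. That goes too far: the urgent care or emergency item covers any reason, so it picks up non-serious events that led to care. The form content is also not shown. The gap is limited to events without such care, and to dates and causes.

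**Readmission.** The location items and the readmission item largely fix hospital status on the call day. A discharged patient scores 7 on the ordinal scale whatever the oxygen use. What is left is a change of status within 2 days of the target, an ordinary visit window.

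**Primary endpoints.** These are little affected. Infusion-related events are counted within 6 hours, inside the 24-hour minimum stay.

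**Conclusion.** The point holds as a limited, inexpensive improvement to one secondary efficacy endpoint and to part of adverse event capture. As written, the script leaves stop days for recipients on home oxygen known only to a gap of 7 days between calls (3 to 11 with windows). It also leaves adverse events without urgent, emergency or inpatient care unprompted.

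Under the first-oxygen-free-call convention the average error is about 3.6 days per affected patient. The cohort median moves from 9.0 to about 9.0–9.1 days if 15–25% go home on oxygen, and to about 10 if 50% do. These figures rest on an assumed home-oxygen share, assumed distributions and an assumed dating rule. A reader might infer a shift of several days in the median. That would take more than half of recipients going home on oxygen with every one of them called, and the protocol does not state calls for everyone.

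One gap lies outside the script's wording: a recipient discharged on oxygen on or after day 7 has no stated contact, so that stop day is unobserved rather than interval-censored.

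**What to change.** Add to the recipient script and the Case Report Form:

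1. the last day of oxygen use;
2. the date and reason of each urgent care or emergency visit and each readmission;
3. the donor script's question on new health concerns.

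Use these dates for the oxygen endpoint and to set hospital status on the target day rather than the call day. In the Statistical Plan, state that where no stop date is obtained the time is analysed as interval-censored, or that the proportion off oxygen at days 7, 14, 21 and 28 is reported instead.

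New wording does not reach recipients discharged on oxygen on or after day 7. Either contact them on the same schedule, or state in the report that their stop dates are censored at discharge.

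The cost is script and form wording, about a minute per call and some recall error in dates. No extra calls are needed unless follow-up is extended to later discharges.
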